### 4.3. Exploratory Objectives

**Table PYAD.4.3. Exploratory Objectives of Part 1 of Study J2X-MC-PYAD(c) in Participants Negative at Baseline for SARS-CoV-2 RT-PCR and Serology**

Objectives	Endpoints
Exploratory	
Compare time to improvement to mild severity symptoms in participants who develop moderate or worse severity a COVID-19	
 
Time to improvement to mild severitya.
 

Characterize COVID-19 illness and severity according to NIAID ordinal scale(s)	
 
Worst score on NIAID ordinal scale(s).
 

Characterize SARS-CoV-2 viral endpoints in those participants that become RT-PCR positive.	
 
Proportion of participants that achieve SARS-CoV-2 clearance within 1, 2, or 3 weeks of positive RT-PCR
 
Time to SARS-CoV-2 clearance
 

Characterize emergence of viral resistance to LY3819253	
 
Comparison from the first positive sample to at least the last positive sample in a subset of participants.
 

Compare the duration of hospitalization due to COVID-19	
 
Cumulative days of hospitalization in those who are hospitalized due to COVID-19.
 

Abbreviations: COVID-19 = coronavirus disease – 2019; NIAID = National Institute of Allergy and Infectious Diseases; RT-PCR = reverse transcription – polymerase chain reaction; SARS-CoV-2 = severe acute respiratory syndrome coronavirus 2.

a as defined in Table 1 of the protocol

**Table PYAD.4.4. Exploratory Objectives of Part 1 of Study J2X-MC-PYAD(c) in Participants Positive at Baseline for SARS-CoV-2 RT-PCR and Negative at Baseline for Serology**

Objectives	Endpoints
Exploratory	
Compare the incidence of moderate or worse severity COVID-19 in participants without moderate or worse severity a COVID-19 at baseline	
 
Cumulative incidence of moderate or worse severity COVID-19; defined as moderate or worse disease severitya within 21 days of baseline.
 

Compare the incidence of COVID-19 in participants who are asymptomatic a baseline.	
 
Cumulative incidence of COVID-19; defined as mild or worse disease severitya within 21 days of baseline
 

Compare time to improvement to mild severity symptoms a in participants who have at baseline, or develop, moderate or worse COVID-19.	
 
Time to improvement to mild severitya.
 

Compare the frequency of hospitalization due to COVID-19	
 
Proportion of participants who are hospitalized due to COVID-19
 

Characterize clinical status for participants.	
Proportion (percentage) of participants who experience these events:
 
 
COVID-19 related hospitalization (defined as <math>\geq 24</math> hours of acute care),
 
COVID-19 related emergency room visit, or
 
death
 

Characterize COVID-19 illness and severity according to NIAID ordinal scale(s)	
 
Worst score on a NIAID ordinal scale(s)
 

Compare the mortality due to COVID-19	
 
Proportion of participants who die due to COVID-19.
 

Characterize SARS-CoV-2 viral endpoints in those participants that become RT-PCR positive.	
 
Proportion of participants that achieve SARS-CoV-2 clearance within 1, 2, or 3 weeks of baseline.
 
Time to SARS-CoV-2 clearance.
 

Characterize emergence of viral resistance to LY3819253	
 
Comparison from baseline to at least the last positive sample in a subset of participants.
 

Objectives	Endpoints
Compare the duration of hospitalization due to COVID-19	
 
Cumulative days of hospitalization in those who are hospitalized due to COVID-19.
 

Abbreviations: COVID-19 = coronavirus disease – 2019; NIAID = National Institute of Allergy and Infectious Diseases; RT-PCR = reverse transcription – polymerase chain reaction; SARS-CoV-2 = severe acute respiratory syndrome coronavirus 2.

a as defined in Table 1 of the protocol

**Table PYAD.4.5. Exploratory Objectives of Part 2 of Study J2X-MC-PYAD(c) in Participants in the Treatment Cohort who are Positive at Baseline for SARS-CoV-2 RT-PCR and Negative at Baseline for Serology**

Objectives	Endpoints
Exploratory	
Evaluate the frequency of hospitalization due to COVID-19	
 
Proportion of participants who are hospitalized due to COVID-19
 

Characterize clinical status for participants.	
Proportion (percentage) of participants who experience these events:
 
 
COVID-19 related hospitalization (defined as <math>\geq 24</math> hours of acute care),
 
COVID-19 related emergency room visit, or
 
death
 

Characterize COVID-19 illness and severity according to NIAID ordinal scale(s)	
 
Worst score on a NIAID ordinal scale(s)
 

Evaluate the mortality due to COVID-19	
 
Proportion of participants who die due to COVID-19.
 

Characterize SARS-CoV-2 viral endpoints.	
 
Proportion of participants that achieve SARS-CoV-2 clearance within 8 or 29 days of baseline.
 
Time to SARS-CoV-2 clearance.
 

Characterize emergence of viral resistance to LY3819253 or LY3832479	
 
Comparison from baseline to at least the last positive sample in a subset of participants.
 

Evaluate the duration of hospitalization due to COVID-19	
 
Cumulative days of hospitalization in those who are hospitalized due to COVID-19.
 

Abbreviations: COVID-19 = coronavirus disease – 2019; NIAID = National Institute of Allergy and Infectious Diseases; RT-PCR = reverse transcription – polymerase chain reaction; SARS-CoV-2 = severe acute respiratory syndrome coronavirus 2.

a as defined in Table 1 of the protocol

**Table PYAD.4.6. Exploratory Objectives of Part 3 of Study J2X-MC-PYAD(c) in Participants Positive at Baseline for SARS-CoV-2 RT-PCR and Negative at Baseline for Serology**

[figure not shown]
Objectives	Endpoints
Exploratory	
Compare the frequency of hospitalization due to COVID-19	
 
Proportion of participants who are hospitalized or experience death due to COVID-19
 

Characterize clinical status for participants.	
Proportion (percentage) of participants who experience these events:
 
 
COVID-19 related hospitalization (defined as <math>\geq 24</math> hours of acute care),
 
COVID-19 related emergency room visit, or
 
Death due to COVID-19
 

Characterize COVID-19 illness and severity according to NIAID ordinal scale(s)	
 
Worst score on a NIAID ordinal scale(s)
 

Characterize the mortality due to COVID-19	
 
Proportion of participants who die due to COVID-19.
 

Characterize SARS-CoV-2 viral endpoints in those participants that become RT-PCR positive.	
 
Proportion of participants that achieve SARS-CoV-2 clearance within 8 or 29 days of baseline.
 
Time to SARS-CoV-2 clearance.
 

Characterize emergence of viral resistance to LY3819253	
 
Comparison from baseline to at least the last positive sample in a subset of participants.
 

Evaluate the duration of hospitalization due to COVID-19	
 
Cumulative days of hospitalization in those who are hospitalized due to COVID-19.
 

Additional exploratory objectives not previously defined in the protocol are described in Section [6.16.2](#).

[figure not shown]
## 5. Study Design

### 5.1. Summary of Study Design

[figure not shown]
This is a Phase 3, randomized, double-blind, placebo-controlled, single-dose study in skilled nursing and assisted living facility residents and staff to evaluate the efficacy and safety of LY3819253, alone and in combination with LY3832479, in preventing SARS-CoV-2 infection and COVID-19.

**Figure PYAD.5.1. Overview of participant flow from time of Index Case at a facility to completion of follow-up for Part 1 of the study**

**Figure PYAD.5.2. Overview of participant flow from time of Index Case at a facility to completion of follow-up for Part 2 of the study**

**Figure PYAD.5.2. Overview of participant flow from time of Index Case at a facility to completion of follow-up for Part 2 of the study**

### 5.1.1. Screening Period

The screening period for each site in Parts 1 and 2 opens when an SARS-CoV-2 index case at the facility is confirmed. A confirmed index case is the first direct SARS-CoV-2 detection result reported at a facility. Screening, randomization and IP administration must be completed within up to 7 days from the index case.

Screening and Day 1 may occur on the same day.

Interested participants or their legal representative will sign the appropriate informed consent document(s) prior to completion of any procedures.

The investigator will review symptoms, risk factors, and other noninvasive inclusion and exclusion criteria prior to any invasive procedures. If the participant is eligible after this review, then the site will perform the invasive procedures to confirm eligibility.

In Part 3, the screening period for each participant starts at the signing of the ICF. Screening, randomization, and IP administration must be completed within 7 days from signing the ICF.

### 5.1.2. *Evaluation Period*

The evaluation period begins when the participant completes screening and is enrolled in the study. Participants will be randomized to placebo or LY3819253 in Part 1. In Part 2, participants will be randomized to placebo, LY3819253, or LY3819253 in combination with LY3832479. In Part 3, participants will be randomized to LY3819253 or LY3819253 in combination with LY3832479. Assessments and procedures will be conducted as described in the Schedule of Activities (SoA; Section 1.3 of the protocol).

If a participant is hospitalized, efforts will be made to retrieve hospital records and report procedures and assessments according to the SoA, as feasible.

### **5.1.3. Follow-up Period**

For Part 1 and for the Prevention Cohort in Part 2, post-treatment follow-up assessments will be conducted at Days 85, 141, and 169 according to the SoA.

For the Treatment Cohort in Part 2 and for all participants in Part 3, a post-evaluation follow-up assessment will be conducted at Day 85 according to the SoA.

Strategies to manage infection risks and reduce the burden of return visits may be used by sites, such as remote visits.

## **5.2. Determination of Sample Size**

For Part 1, an estimated 33 events are needed to show superiority of LY3819253-4200mg over placebo in each of the primary and key secondary endpoints, using the formula by Schoenfeld (1983). An average sample size of approximately 1300 participants who are SARS-CoV-2 PCR negative and serology negative at baseline is expected to obtain the needed number of events for each endpoint.

For Part 2, an estimated 56 events in the Prevention Cohort are needed to show superiority over placebo for either LY3819253-700mg or LY3819253-350mg+LY3832479-700mg in each of the primary and key secondary endpoints. Approximately 2000 participants on average will be randomly assigned to study intervention such that approximately 1700 participants are randomized in the Prevention Cohort with the goal of achieving approximately 56 events on each of the primary and key secondary endpoints.

The maximum sample size for this study is approximately 5000 participants in the intent-to-treat (ITT) population.

Participants will be residents and staff of skilled nursing and assisted living facilities. Globally, there are many reports of the rapid spread of COVID-19 amongst residents of skilled nursing facilities following identification of an index case, with high associated rates of morbidity and mortality (Arons et al. 2020; Grabowski). Given that residents at these facilities are at higher risk for having a more severe disease course of COVID-19, this will be an important population to participate in the study. Therefore, a minimum of 300 residents will be enrolled.

Operationally, this will be accomplished, when possible, by identifying facilities where approximately half of the participants interested in the study are residents.

For sample size determination for Part 1, the following assumptions were used:

- 1) two-sided significance level of 0.05;
- 2) 90% power for the primary and key secondary endpoints;
- 3) an 8-week placebo group event rate of 4.0% for moderate or worse severity COVID-19;
- 4) a risk ratio of 0.33 between LY3819253 and placebo in terms of the primary and key secondary endpoints.

For sample size determination for Part 2, the following assumptions were used:

- 1) two-sided significance level of 0.025;
- 2) 90% power for the primary and key secondary endpoints;
- 3) an 8-week placebo group event rate of 5.3% for moderate or worse severity COVID-19;
- 4) a risk ratio of 0.33 between active drug and placebo in terms of the primary and key secondary endpoints.

Due to the dynamic nature of the pandemic, Part 3 will enroll at least 30 participants and up to approximately 500 participants randomized to either LY3819253 700 mg or LY3819253 700 mg + LY3832479 1400 mg. Part 3 of the study is considered exploratory and is not powered for inference between the two treatment arms.

## 5.3. Method of Assignment to Treatment

### 5.3.1. Randomization

All participants will be centrally randomized to study intervention using an interactive web-response system (IWRS). Before the study is initiated, the log-in information and directions for the IWRS will be provided to each site.

Block randomization within each site will be used to achieve between-group comparability, and participants will be stratified by role within the facility (resident versus facility staff), and by sex.

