This amendment will allow participants with COVID-19 to enroll in Part 3 (treatment only) of Study PYAD who have recovered from prior COVID-19 infection, or have received prior administration of convalescent plasma, monoclonal antibody, or vaccine for SARS-CoV-2. Inclusion will allow for collection of data to explore safety of treatment of LY3819253 alone or in combination with LY3832479 in any of these participant populations.

Section # and Name	Description of Change	Brief Rationale
Section 1.3.1 Part 1 and Prevention Cohort of Part 2	Updated “Prior treatments of special interest” to collect prior use of SARS-CoV-2 vaccine.	The SARS-CoV-2 vaccine is now allowed.
Section 1.3.2 Part 2 Treatment Cohort and Part 3		
2.2 Background	Added background on PYAB interim results.	Emerging data.
2.3 Benefit/Risk Assessment	Updated risk information for LY3819253.	Emerging data.
4.2 Scientific Rationale for Study Design	Added rationale for participants who have received the SARS-CoV-2 vaccine. Added language for Part 3 to reflect that participants who were in independent living situations at the facilities could be enrolled.	Vaccines are now available to the public and those who received a vaccine are allowed in the study. Clarification.
5.2 Exclusion Criteria	Updated Criteria 7, 8, 9, 11, 12, and 13.	This amendment will allow participants with COVID-19 to enroll in Part 3 (treatment only) of the study having recovered from prior COVID-19 infection, or having received prior administration of convalescent plasma, monoclonal antibody, or vaccine for COVID-19. Inclusion will allow for collection of data to explore safety of treatment of LY3819253 alone or in combination with LY3832479 in any of these participant populations.

Section # and Name	Description of Change	Brief Rationale
6.3 Measures to Minimize Bias: Randomization and Blinding	Added stratification factor for whether a participant received a vaccine or not prior to screening	The SARS-CoV-2 vaccine is now allowed
11 References	Added Chen et al. 2020 reference	Source for information in Section 2.3

Table of Contents

1. Protocol Summary	8
1.1. Synopsis	8
1.2. Schema	15
1.3. Schedule of Activities (SoA)	17
1.3.1. Part 1 and Prevention Cohort of Part 2	17
1.3.2. Part 2 Treatment Cohort and Part 3	24
2. Introduction	28
2.1. Study Rationale	28
2.2. Background	28
2.3. Benefit/Risk Assessment	29
3. Objectives and Endpoints.....	31
4. Study Design	37
4.1. Overall Design	37
4.1.1. Screening Period	37

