Monoclonal antibodies may provide benefit for the treatment of mild to moderate COVID-19 (FDA EUA fact sheet 2020). Therefore, prior to randomization in Part 2, participants will receive a POC test for SARS-CoV-2 infection. Participants will be assigned to either Prevention or Treatment Cohorts based on the result of this POC test. Despite using a SARS-CoV-2 POC test during screening to assign participants to either the Prevention or Treatment cohorts, baseline SARS-CoV-2 RT-PCR and serology test results will be used to determine the study analysis populations. Refer to Section 9.3, Populations for Analyses, for further information on study analysis populations and treatment arms.

Part 3 of the study is a two-arm, outpatient, open-label, exploratory cohort evaluating the efficacy and safety of LY3819253 and LY3819253 in combination with LY3832479 in participants positive for SARS-CoV-2 with or without symptoms in staff and residents who are at higher risk for more severe disease and hospitalization in skilled nursing and assisted living facilities. For Part 3 only, participants who were in independent living situations at the facilities could be enrolled to the study.

SARS-CoV-2 vaccines are now available to the public. Those who received a vaccine are now allowed in the study to assess the safety of LY3819253 and LY3832479 after a person received a SARS-CoV-2 vaccine.

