5.2. Exclusion Criteria

Participants are excluded from the study if any of the following criteria apply:

7. For Parts 1 and 2, recovered from COVID-19 disease or asymptomatic infection
8. For Parts 1 and 2, a prior history of a positive SARS-CoV-2 serology test
9. For Parts 1 and 2, a history of Convalescent COVID-19 plasma treatment
10. Are an inpatient in hospital
11. For Parts 1 and 2, participation in a previous SARS-CoV-2 vaccine trial or received an approved SARS-CoV-2 vaccine
12. For Parts 1 and 2, previous receipt of SAR-CoV-2-specific monoclonal antibodies
13. Have participated, within the last 30 days, in a clinical study involving an investigational product. If the previous investigational product has a long half-life, 5 half-lives or 30 days (whichever is longer) should have passed. This criterion does not apply to products described in Criteria 9, 11, and 12.
14. Are pregnant or breast feeding
15. Are concurrently enrolled in any other type of medical research judged not to be scientifically or medically compatible with this study
16. Have known allergies to related compounds of LY3819253, LY3832479 or any components of the formulation
17. Suspected or proven serious, active bacterial, fungal, viral, or other infection that in the opinion of the investigator could constitute a risk when taking investigational product
18. Have any serious concomitant systemic disease, condition or disorder that, in the opinion of the investigator, should preclude participation in this study.

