6.3. Measures to Minimize Bias: Randomization and Blinding

Randomization

Participants who meet all criteria for enrollment will be randomized on Day 1 as follows:

- In Part 1, 1:1 to double-blind treatment
- In Part 2, will be allocated as follows:
 - Prevention Cohort: 1:1:1 to double blinded treatment
 - Treatment Cohort: 1:1, as described in Part 2 Treatment Cohort below
- In Part 3, 1:1 to open label treatment

To achieve between-group comparability, block randomization within each facility will be used. Randomized participants within the facility will be stratified by role within the facility (resident versus facility staff), by sex, and whether or not the participant received a SARS-CoV-2 vaccine prior to screening (in Part 3 only).

All participants will be centrally randomized to study intervention using an Interactive Web Response System (IWRS). Before the study is initiated, the log in information and directions for the IWRS will be provided to each site.

Blinding

Part 1 and Part 2 Prevention Cohort

Part 1 and Part 2 are blinded. Neither participants, nor investigators, nor the sponsor study team will be aware of treatment assignments prior to the final database locks at the conclusion of the study, except as described in the following note.

Note: It is possible that some participants will have the SARS-CoV-2 negative result on the screening point of care test, but could be positive on the baseline SARS-CoV-2 PCR test. The results from the baseline PCR test will not be available until after the participant is randomized. Once positive results are known from the baseline PCR test, these participants will be unblinded and have the option to continue to be followed for safety according to the Prevention Cohort SoA. This table describes general procedures for unblinding.

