Part 2 Prevention	
Definition: All participants in the Enrolled/Intent-to-Treat population in the Prevention Cohort in Part 2 who are SARS-CoV-2 RT-PCR negative and serology negative at baseline.
 
Purpose: Used for efficacy and health outcomes analyses.
 
Treatment Groups (Short Label): 700 mg LY3819253, 350 mg LY3819253 + 700mg LY3832479, and placebo
 
Inferential Comparisons: LY3819253 versus placebo, LY3819253 + LY3832479 versus placebo

Part 1 Treatment	
Definition: All participants in the Enrolled/Intent-to-Treat population in Part 1 who are SARS-CoV-2 RT-PCR positive at baseline and serology negative at baseline.
 
Purpose: Used for efficacy and health outcomes analyses.
 
Treatment Groups (Short Label): 4200 mg LY3819253 (4200 LY) and placebo (Pbo)
 
Inferential Comparisons: LY versus placebo

Part 2 Treatment	
Definition: All participants in the Enrolled/Intent-to-Treat population in the Treatment Cohort in Part 2 who are POC positive, RT-PCR positive, and SARS-CoV-2 serology negative at baseline.
 
Purpose: Used for efficacy and health outcomes analyses.
 
Treatment Groups (Short Label): 700 mg LY3819253, 350 mg LY3819253 + 700mg LY3832479, and placebo
 
Inferential Comparisons: LY3819253 versus placebo, LY3819253 + LY3832479 versus placebo

Part 3 Treatment	
Definition: All participants in the Enrolled/Intent-to-Treat population in Part 3 who are RT-PCR positive, and SARS-CoV-2 serology negative at baseline.
 
Purpose: Used for efficacy and health outcomes analyses.
 
Treatment Groups (Short Label): 700 mg LY3819253 and 700 mg LY3819253 + 1400mg LY3832479
 
Inferential Comparisons: LY3819253 versus LY3819253 + LY3832479 (not powered for formal inference)

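### SAP Version 4 predates the current protocol's Part 3 vaccine stratum and pre-specifies no safety summary for the vaccinated or previously exposed participants now admitted

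*SAP*

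**What the plan says.** **Protocol, current amendment.** Section 6.3 blocks randomization within facility and stratifies by role, by sex and by "whether or not the participant received a SARS-CoV-2 vaccine prior to screening (in Part 3 only"). Section 4.2 gives the reason for admitting vaccinated people: "Those who received a vaccine are now allowed in the study to assess the safety of LY3819253 and LY3832479" after vaccination. The amendment summary at the front gives the same aim for people who have recovered from COVID-19 or received convalescent plasma, a monoclonal antibody or a vaccine: "Inclusion will allow for collection of data to explore safety of treatment of LY3819253 alone or in combination with LY3832479". Section 5.2 carries this through by limiting the relevant exclusions, for example "For Parts 1 and 2, recovered from COVID-19 disease or asymptomatic infection" and "For Parts 1 and 2, participation in a previous SARS-CoV-2 vaccine trial or received an approved SARS-CoV-2 vaccine". Section 9.3 defines a Serology-Positive population across all enrolled participants.

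**SAP Version 4.** Section 5.3.1 says only that "participants will be stratified by role within the facility (resident versus facility staff), and by sex". Section 6.1.4 spells out role and sex as the stratification factors in the logistic model for binary efficacy endpoints, and names facility, role and sex in the MMRM and ANCOVA. The general safety models in Section 6.12 carry no stratification factor. Section 6.13 summarises adverse events by role and lists no subgroup for vaccination, prior infection or serology. Table PYAD.6.1 defines Part 3 Treatment as "All participants in the Enrolled/Intent-to-Treat population in Part 3 who are RT-PCR positive, and SARS-CoV-2 serology negative at baseline" and has no Serology-Positive population.

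**The concern.** The protocol names a purpose for admitting these participants and randomizes on one of their defining features. The analysis plan beside it has no table or model term that uses that feature.

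Part 3 is open label. If safety by vaccination or prior exposure is left to later choice, the splits will be chosen by people who can see events by arm. A descriptive table fixed in advance avoids that. A second, smaller issue is that a factor used in the Part 3 randomization is not named in the models that list their covariates.

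**Working it through.** No sample-size, power or alpha figure in the plan bears on this point, and Part 3 is stated to be unpowered. The check is a comparison of texts, followed by a short precision calculation.

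**1. Timing.** The SAP revision history dates Version 4 to 7-Dec-2020 and ties it to amendment (c). The current protocol lists amendment (c) in its amendment history (Appendix 9) and cites data to 31 December 2020 (Section 2.3). The protocol is therefore the later document. No later SAP was supplied.

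**2. Side by side, Part 3.**

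| Item | Current protocol | SAP Version 4 |
|---|---|---|
| Stratification factors | Role, sex, prior vaccination (6.3) | Role, sex (5.3.1) |
| Models that list their factors | Deferred to the SAP for Part 3 | Facility, role, sex (6.1.4) |
| Safety split | Purpose stated (4.2, amendment summary); no table specified | By role only (6.13) |
| Serology-positive participants | Population defined (9.3) | Not in Table PYAD.6.1 |

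**3. Data available.** Schedule 1.3.2 records SARS-CoV-2 vaccination at any time before screening, and takes serology before dosing on Day 1. Prior infection depends on medical history. The other prior treatments of special interest are recorded for the last two weeks only, and that list names neither convalescent plasma nor antibody.

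**4. Strata.** Role by sex gives 2 × 2 = 4 cells per facility. Adding vaccination gives 2 × 2 × 2 = 8.

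**5. What a split table could show.** Part 3 size is 30 to about 500 (Protocol 9.2, SAP 5.2). The vaccinated share v is not given, so 10% to 50% is assumed. The number vaccinated over both arms is n = N × v. With zero events, the exact one-sided 95% upper bound on an event rate is 1 − 0.05^(1/n).

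| N | v | n | Upper bound, zero events |
|---|---|---|---|
| 30 | 10% | 3 | 63% |
| 30 | 50% | 15 | 18% |
| 500 | 10% | 50 | 5.8% |
| 500 | 50% | 250 | 1.2% |

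With 1:1 allocation, the average number of vaccinated participants per arm and role-by-sex cell is n/(2 × 4), before any split by facility. That is 3/8 = 0.375 at the low extreme and 250/8 = 31.25 at the high extreme.

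**The case against.** The strongest reply is that this is an older SAP beside a newer protocol, that the protocol already covers much of the ground, and that Part 3 is exploratory.

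- **Generic wording.** Table PYAD.6.3 and Sections 6.16.1.2, 6.16.1.6, 6.16.2.1 and 6.16.2.5 refer to the randomization stratification factors without naming them, and could take in vaccination. This stands in part: a reader might infer that every SAP model excludes vaccination, and the text does not show that. But Sections 5.3.1 and 6.1.4 define the factors as role and sex, and the Section 6.12 safety models use none.
- **The question remains answerable.** A reader might infer that safety in these participants cannot be assessed. That goes too far. Vaccine status is collected, adverse events are listed by participant (Protocol 9.4.6.1), deaths and serious events get narratives (SAP 6.12.4), and Section 6.13 allows further subgroups without a SAP amendment. These are data and permission, not a plan.
- **Protocol-level safety plan.** Protocol Section 3 says that Part 3 safety will be characterized in the overall and the analysis populations, and Section 9.3 defines Serology-Positive. So serology-positive participants are not confined to pooled tables at protocol level. This stands; the defect is that the SAP table omits that population.
- **Prior infection as a stratum.** A reader might infer that previously infected participants are also stratified on. They are admitted, but only vaccination is a stratum.
- **Loss from the efficacy set.** A reader might infer that most vaccinated participants drop out of Part 3 Treatment. Only serology-positive participants do, and the documents do not say how many vaccinated people would be positive. Protocol and SAP agree on a serology-negative set, so repeating outcomes regardless of serology would be a preference.
- **Exploratory status.** Part 3 has no placebo arm and no powered comparison, and a vaccinated-versus-unvaccinated contrast would not be randomized. This lowers the importance of the covariate. It does not remove the case for descriptive tables, which need no power.

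**Conclusion.** The gap is real and moderate in size. In the documents supplied, the SAP was not aligned with the current protocol. It does not name the Part 3 vaccine stratum, plans no safety summary by vaccine status or prior exposure, and omits the Serology-Positive population. No pre-specified SAP analysis therefore addresses the reason given for admitting these participants.

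The missing safety split is the main point. The missing covariate is minor, because Part 3 is open label, exploratory and unpowered.

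No figure in the plan changes. The counts of 3 to 250 vaccinated participants rest on the assumed share, and all of them would still be reported in the pooled Part 3 Safety population. The verdict also assumes that no later SAP exists; one written for the current amendment could already have closed the gap.

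**What to change.** Update the SAP to the current amendment:

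1. In Section 5.3.1, list prior SARS-CoV-2 vaccination as a Part 3 stratification factor.
2. In Section 6.1.4, include it in the Part 3 comparison models where estimable, and state what is dropped first when cells are sparse. Near 30 participants, with facility also in the model, it may not be estimable.
3. In Sections 6.12 and 6.13, add descriptive Part 3 Safety tables (treatment-emergent events, serious events, deaths, hospitalization) by arm for prior vaccination (yes/no), and for baseline serology or recorded prior infection. State that near minimum enrolment these serve as listings.
4. Add the Serology-Positive population to Table PYAD.6.1.
5. Split by prior plasma or antibody only if that history is confirmed to be captured beyond the two-week look-back.

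The cost is a SAP revision and a few tables. Vaccine status and baseline serology are already collected; item 5 needs a check of the case report form. The one drawback is sparse cells at low enrolment.
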